3.4. Stratification Factors and Covariates

Subjects will be randomly assigned to treatment groups in a 1:1 ratio (Protocol V1.0) and a 2:1 ratio (Protocol V3.3 and beyond) using stratified randomization via an interactive voice or web-based response system (IRT). Stratification will be based on the following variables:

- Type of infection (non-ventilated HABP vs. ventilated HABP).
- Acute Physiology and Chronic Health Evaluation II (APACHE II) scores (<15 versus ≥ 15).
- Country/Region (China & Rest of the World).

If there is a difference in the stratification factors between the IRT and the EDC, the value recorded in the EDC will be used in the analysis. In addition, this difference will be presented in the statistical analysis.

For efficacy endpoints, stratification variables will be included as covariates in the efficacy analysis model.

3.5. Missing Data and Outliers

3.5.1. Missing Data

As a general rule, missing data are not filled in unless otherwise specified. The exceptions are listed below.

Section 9.1.5.2 describes how to handle missing or incomplete AE start dates. The treatment of prior and concomitant medications is described in Section 7.1. For missing primary estimate target analyses, the fill rules are described in Section 8.1.2. For missing microbiologic data, the fill rule is described in Section 3.6.2. For missing clinical outcomes, microbiologic outcomes, and overall assessment results, the rules for filling in are described in Sections 8.2.2.1, 8.2.3.1, and

8.2.4.1. Sections 8.3.1 and 5.2 describe the treatment of incomplete dates for exploratory endpoints. Details of the filling of these missing data can be found in the relevant sections of this document.

3.6. Data Processing and Derivation Rules

The rules regarding PK data are detailed in chapter 10.

3.6.1. Safety and Efficacy Data

Continuous safety and efficacy and data will be filled in as follows:

- If the data is reported as " x ", a value 1 unit less than x will be used to calculate the descriptive statistic. For example, if the reported values are < 50 and < 5.0 , then 49 and 4.9, respectively, will be used to calculate the summary statistic. An exception to this rule is if the reported value is < 1 or < 0.1 , etc. If the reported value is < 1 or < 0.1 , then 0.9 or 0.09 will be used to calculate the summary statistic, respectively.
- If the data is reported as " $> x$ ", a value 1 unit greater than x will be used to calculate the descriptive statistic. Values with a decimal point will follow the same logic as above. For subjects with O2 saturation, Basophils, Eosinophils, Hematocrit, Lymphocytes, Monocytes and Neutrophils, the percentages will be calculated. Neutrophils, with the maximum percentage not exceeding 100%.
- If the data are reported as " $\leq x$ " or " $\geq x$ ", x will be used to calculate descriptive statistics.

3.6.2. Microbiology Data

Microbiology data include blood cultures and lower respiratory sample cultures. Microbiological sample collection and manipulation are detailed in the sample manipulation manual.

Statistical analysis of microorganisms associated with lower respiratory tract samples is based on samples collected by BAL, mini-BLA, or PBS, as well as qualifying endotracheal aspirates and coughed sputum (which should meet < 10 squamous epithelial cells and > 25 neutrophils). Definitions of eligibility are detailed in section 7.5.6.2 of the clinical protocol. During bacteremia analysis, any pathogenic organism detected in blood culture samples will be defined as bacteremia (with the following blood isolates considered non-pathogens: *Corynebacterium* spp., *Propionibacterium* spp. [with the exception of *Propionibacterium acnes*] and other diphtheroid; as well as *Bacillus* spp.)

The susceptibility of the pathogenic bacteria to the test drug and/or the control drug will be analyzed based on the results of the central laboratory drug sensitivity assay.

The susceptibility of the test drug IMI-XNW4107 was determined according to the provisional fold point of IMI-XNW4107, a β -lactamase inhibitor, which acts in combination with imipenem by restoring the activity of imipenem. Therefore, the interim discount points for IMI-XNW4107 against *Escherichia coli*, *Pseudomonas aeruginosa*, and *Acinetobacter baumannii* were

determined according to the CLSI discount points for imipenem (1, 2, and 2 ug/mL, respectively). Previous population pharmacokinetic and Monte Carlo simulation analyses of the probability of attainment of the antimicrobial PK/PD target values support a >90% probability of attainment of the PK/PD target values at these interim fold points for all dose-delivery groups in the XNW4107-302 study. For other pathogenic bacteria, the highest provisional fold point (2 ug/mL) was determined for these 3 pathogens. That is, susceptibility was determined at MIC=2 ug/mL for all pathogenic bacteria except for Escherichia coli, for which susceptibility was determined at MIC=1 ug/mL. If the minimum inhibitory concentration (MIC) of the test drug (IMI-XNW4107) for a particular pathogen \leq break point, the test drug will be determined to be sensitive for that pathogen.

For all pathogens missing IMI/REL susceptibility data, impute using IMI susceptibility results (only for pathogens with IMI susceptibility reported as Susceptible [S]. Specifically: if IMI/REL susceptibility is missing but IMI susceptibility data exists and is Susceptible [S], then IMI/REL susceptibility for that pathogen shall be imputed as Susceptible [S]).

The analysis related to microbiological data is mainly based on the test results of the central laboratory, and if the pathogen names of the local laboratory and the central laboratory are different, the pathogen names of the central laboratory are used for analysis. However, if the pathogen name is identified in the local laboratory data but not mailed to the central laboratory for various reasons, the pathogen name reported by the local laboratory is used for filling. In this case, the MIC will be considered unknown. For pathogens sent repeatedly by the local laboratory, if the names of the pathogens are consistent between the two mailings (using the name tested by the central laboratory), use the first mailing of pathogen data; if the names of the pathogens are not consistent between the two mailings, use the second mailing of pathogen data.

Definition of carbapenem-resistant pathogens: pathogenic bacteria that are resistant to any of the imipenem or meropenem carbapenem antimicrobials.

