8.2.3. Microbiological Outcomes

Lower respiratory tract sample and blood culture data will be collected during the study and will be used in addition to the clinical response to programmatically assess the microbiological outcomes as defined below and carried out on EOT, TOC, and LFU visit.

- **Microbiological success** is based on the following rules:
 - **Eradication:** Absence of the baseline Gram-negative pathogen from an appropriate clinical specimen.
 - **Presumed eradication:** Absence of appropriate post-baseline culture material in a subject, but judged to be a clinical success.
- **Microbiological failure** is based on the following:
 - **Persistence:** Continued presence of the baseline Gram-negative pathogen from an appropriate clinical specimen. Persistence at EOT or TOC will be carried forward.
 - **Presumed persistence:** Absence of appropriate post-baseline culture material in a subject, but judged to be a clinical failure.
 - **Recurrence:** Recurrence of the baseline Gram-negative pathogen from an appropriate clinical specimen taken after TOC and the TOC culture shows eradication.
 - **Indeterminate:** No culture obtained from an appropriate clinical specimen and no clinical outcome is determined.

Pathogens first appearing after baseline in subjects with a different baseline pathogen are categorized as described below and will be considered separately from microbiological response.

- **Superinfection:** Isolation of new pathogen(s) (other than the original baseline pathogen[s]) from an appropriate clinical specimen during treatment with study drug that is accompanied by new or worsening signs and symptoms of infection requiring alternative antimicrobial therapy
 - Superinfection were assessed at the EOT visit with the rule that new pathogens other than the original baseline pathogen were isolated from appropriate lower respiratory tract clinical samples during the EOT visit or prior study drug therapy and were clinically assessed as failures.
- **New infection:** Isolation of new pathogen(s) (other than the original baseline pathogen[s]) from an appropriate clinical specimen after completion of study drug treatment that is accompanied by new or worsening signs and symptoms of infection requiring alternative antimicrobial therapy.

New infections are evaluated at the TOC and LFU visits with the rules:

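### SAP 3.6.2 has no rule for matching a centrally named isolate with a locally named one, or for isolates mailed but not recovered, so a persisting baseline pathogen can be scored as eradicated

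*SAP*

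**What the plan says.** **Naming (SAP 3.6.2).** Central-laboratory results are the main basis. Where the two laboratories give different names, "the pathogen names of the central laboratory are used for analysis". The exception applies "if the pathogen name is identified in the local laboratory data but not mailed to the central laboratory for various reasons"; then "the pathogen name reported by the local laboratory is used for filling". The SAP adds: "In this case, the MIC will be considered unknown". For a pathogen sent twice, the first mailing is used if the names agree; "if the names of the pathogens are not consistent between the two mailings, use the second mailing of pathogen data".

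**Outcome (SAP 8.2.3).** Cultures and clinical response are used to "programmatically assess the microbiological outcomes as defined below". Eradication is "Absence of the baseline Gram-negative pathogen from an appropriate clinical specimen". Persistence is the same pathogen still present. If there is no suitable post-baseline culture, the result follows the clinical outcome (presumed eradication or presumed persistence). Superinfection begins with "Isolation of new pathogen(s) (other than the original baseline pathogen[s]) from an appropriate clinical specimen during treatment with study drug"; new infection is the equivalent after treatment. Both are operationalised with clinical failure, and colonization with clinical success.

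**Related rules.** SAP 3.6.2 takes susceptibility to the study drugs from the central laboratory. SAP 3.2.4 requires every baseline Gram-negative pathogen in micro-MITT to be susceptible to both drugs. SAP 3.7.5.2 uses all cultures collected within a post-baseline nominal visit. SAP 8.2.4 takes the microbiological component of overall outcome from the central laboratory and does not mention the local fallback.

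**The concern.** Whether a baseline pathogen has persisted depends on whether two isolates are called the same thing. The naming rule works isolate by isolate, so one subject can have a central name at baseline and a local name later. Nothing in SAP 3.6.2 links the two, and SAP 8.2.3 describes a programmed derivation with no adjudication.

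The fallback also turns on mailing rather than on whether a central result exists. Two isolates with the same information (a local identification and no central one) are handled differently: the unmailed one keeps its local name, and the mailed one has no stated rule.

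At stake are microbiological success by subject and by pathogen, overall success, and the superinfection, new-infection and colonization tables. A subject with one baseline pathogen, clinical success and a culture still growing that pathogen could be counted as a microbiological and an overall success.

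**Working it through.** The plan attaches no figure to this rule, so there is nothing to reproduce. The check traces a true persister through the rules and then sizes the effect on assumed inputs.

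**1. Rule trace.** The baseline isolate was mailed and has a central name. The later isolate is the same organism.

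| Later isolate | Name used | Scored as |
|---|---|---|
| Mailed and recovered | Central | Persistence |
| Not mailed, local name equals the baseline central name | Local | Persistence |
| Not mailed, local name differs from the baseline central name | Local | Eradication; plus superinfection or new infection if clinical failure, colonization if clinical success, no new-organism label if clinical outcome is indeterminate |
| Mailed, not recovered | No rule | Depends on the reading (step 3) |

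The third row follows from the rules as written.

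**2. Populations.** An unmailed isolate has unknown MIC, so its susceptibility cannot be shown. Micro-MITT needs all baseline pathogens susceptible to both drugs, and ME is drawn from micro-MITT. In those two populations baseline pathogens therefore carry central names, and the mismatch can come only from an unmailed post-baseline isolate. In extended micro-MITT and CR-MITT one qualifying pathogen is enough (SAP 3.2.6, 3.2.5), so a second, unmailed baseline pathogen can also produce it.

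**3. Mailed but not recovered.** Three readings are open:
- The positive local culture counts, because SAP 3.7.5.2 uses all cultures at the visit: persistence.
- Only central results count, as SAP 8.2.4 suggests: eradication, with no new-organism label.
- There is no suitable culture material: presumed eradication or presumed persistence, following the clinical outcome.

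**4. Size.** All inputs are assumptions; none is in the documents.
- Culture-proven persistence: 20% to 40% of subjects.
- Local and central names discordant: 5% to 15% of isolates.
- Later isolates not mailed: 5% to 20%.
- Mailed isolates not recovered: 2% to 10%.

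Mixed-name route, share of persisting isolates = discordance × not mailed:
- low 0.05 × 0.05 = 0.0025 (0.25%); high 0.15 × 0.20 = 0.03 (3%).

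As a share of subjects = persistence × that share:
- low 0.20 × 0.0025 = 0.0005 (0.05%); high 0.40 × 0.03 = 0.012 (1.2%).

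Non-recovery route, share of subjects = persistence × non-recovery, if every case is read as eradication:
- low 0.20 × 0.02 = 0.004 (0.4%); high 0.40 × 0.10 = 0.040 (4.0%); middle 0.30 × 0.05 = 0.015 (1.5%).

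**5. Effect on a difference.** If a share q of persisters is scored as eradicated in both arms, scored success = 1 − persistence × (1 − q), and a true difference is multiplied by (1 − q). For an assumed 20% versus 30% persistence (10 points):
- mixed-name route, q = 0.0025 to 0.03: 10 × 0.9975 = 9.975 down to 10 × 0.97 = 9.7 points.
- non-recovery route, q = 0.02 to 0.10: 10 × 0.98 = 9.8 down to 10 × 0.90 = 9.0 points.

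**The case against.** **The SAP does not say that an unrecovered isolate means eradication.** A reader might infer this from the not-mailed condition. The text does not support it: central names override only where the two laboratories differ, and with no central name there is no conflict. SAP 3.7.5.2 uses all cultures at the visit, and on another reading clinical failures stay failures. The repeat-mailing rule also shows that isolates could be sent again. This objection stands. On this route the defect is an undefined case, not a wrong rule. It does not touch the mixed-name route.

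**The numbers are ceilings on assumed inputs.** Several cultures may exist at a visit, persistence at EOT or TOC is carried forward, and by-subject success needs every baseline pathogen cleared (SAP 8.2.3.3). Overall success changes only among clinical successes, because a clinical failure is already an overall failure. All of this stands.

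**A threat to the non-inferiority conclusion does not follow.** A reader might infer one from the shrinkage in step 5. The stated hypothesis and 10% margin in SAP 8.1.2.1 concern Day 14 mortality in the MITT population, which uses no culture data. SAP 8.2.3.3 borrows the primary method for microbiological success, but no margin is stated for it.

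**A rule may exist elsewhere.** Protocol 7.5.6 to 7.5.9 cannot be read in the public text, and the sample manual was not supplied, so this cannot be excluded. However, SAP 3.2.4 to 3.2.6 name SAP 3.6.2 as the place for the derivation rules. SAP 3.6.2 cites the manual for sample collection and handling, and protocol 7.5.6.2 for specimen eligibility, not for naming.

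**Conclusion.** The point holds for secondary endpoints. As written, a baseline isolate renamed centrally and a later unmailed isolate of the same organism under its local name are scored as eradication, and often also as a new organism. For isolates mailed but not recovered, the SAP leaves the result open.

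A reader might also infer that an unmailed baseline isolate causes the same error in every population. It cannot do so for a micro-MITT or ME baseline pathogen, for the reason in step 2.

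On the assumed inputs the effect is about 0.05% to 1.2% of subjects by the mixed-name route and at most 0.4% to 4.0% by the non-recovery route. The mixed-name figure assumes that discordance and non-mailing are independent and that the later isolate keeps the earlier local name. Similar errors in both arms would raise both success rates and slightly shrink any true difference. The primary endpoint is unaffected. The change is worth making because it is cheap and the affected endpoints are derived by program.

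**What to change.** Make three changes to the SAP.

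1. Replace the fallback sentence in 3.6.2 with: *If the local laboratory identified an organism and no central identification exists for that isolate, because it was not mailed or was mailed and not recovered, the local identification is used and the MIC is unknown.*
2. Add to 3.6.2: *Where the baseline and post-baseline isolates do not both have a central name, they are the same pathogen if the name of the isolate without a central result matches either the local or the central name of the other isolate; the pathogen is reported under the central name if one exists.*
3. Align the source statement in 8.2.4 with this rule, so that microbiological and overall outcomes use the same data.

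Matching on local names alone would not be enough. If the baseline isolate is X locally and Y centrally, and a later unmailed isolate is Y locally, the present rule correctly gives persistence, and a local-only rule would lose it.

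**Cost.** A few sentences and a change to the derivation program, using data already collected. Where the local laboratory gives two species one name, a few cases will be scored as persistence, which is conservative for success rates. A baseline isolate mailed but not recovered would become a named pathogen with unknown MIC, which can affect micro-MITT membership in subjects with several pathogens. The change should therefore be made before populations are fixed and data unblinded; if it comes after the SAP is final, it should be documented in the clinical study report, as SAP section 1 provides.

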3.7. Analyzing the Interview Window

3.7.1. Definition of Study Day

Study days will be calculated from the subject's randomization date using the following formula:

- Post-randomization study day: assessment date - randomization date + 1
- Study day before randomization: assessment date - randomization date

Thus, study day 1 refers to the date of randomization.

3.7.2. Definition of Follow Up Day

Follow-up days will be defined as the number of days after the last dosing date (FU Day 0) and will only be counted if the collection date is on or after the last dosing date, which will be calculated as follows:

Follow-up day = Date of collection - Last date of administration

3.7.3. Definition of Baseline

Unless otherwise noted, baseline will be defined as the last non-missing outcome prior to the first dose.

For results that were collected on the date of the exam, but not at the time, the screening period will be considered to have occurred prior to the D1 visit in the calculation. For chest imaging results, and microbiology sample culture results, the time of collection needs to be within the time window specified in the following scenarios, and anything beyond that will not be included in the calculation of the baseline.

- Imaging is acceptable for results within 48h prior to randomization;
- Microorganisms can be accepted as samples within 48h prior to randomization to assess contamination not as a baseline.

3.7.4. Analysis Visit Windows

Subject visits may be conducted beyond the window (i.e., beyond the date specified in the protocol), but data collected should be as of the time of that visit requirement (e.g., survival at D28 may be conducted at D30 but collected at D28 and earlier), and the efficacy and safety analyses will be conducted using the nominal visit as documented on the CRF (according to the protocol).

3.7.5. Selection of Data in the Event of Multiple Records in an Analysis Visit

Depending on the method of statistical analysis, only a single value may be required under each nominal visit. For example, a single value is usually required for the change from baseline across visits; whereas for time-to-event analyses, a single value per analytical window is not required.

3.7.5.1. Safety Data

If multiple valid, non-missing measurements exist for each visit, but only a single value is needed, the record will be selected based on the following rules:

- For baseline, the last non-missing value prior to the time of the first administration of the study drug will be selected unless otherwise stated; if no time was recorded, or a time is missing, the value of the last non-missing time prior to the date of the first administration will be selected for inclusion in the calculation. If there are multiple records on the same day with the same time or with no time recorded, the mean value will be the baseline value for continuous data, and for categorical data, the result with the lowest severity (e.g., for electrocardiogram [ECG] safety results, a normal rather than an abnormal result will be selected) will be the baseline value.
- For post-baseline values (only results from nominal visits were considered):

- The record closest to the nominal study date for that visit (for EOT visits, the nominal study date is the last date of administration) will be selected.
- If 2 records are equidistant from the nominal study date, the record with the later study date is selected.
- If there was more than 1 record on the selected study day, the average was taken for continuous data and the most severe record for categorical data, unless otherwise stated.

3.7.5.2. Microbiological Data

If multiple valid, non-missing measurements exist for each nominal visit, the records will be selected based on the following rules:

- For the baseline:
 - Lower respiratory sample cultures: culture results from the most recent non-missing collection of samples prior to the time of first administration of study drug will be selected. Microbiological samples within 48h prior to randomization are acceptable, isolates assessed as contaminated microbiological samples will not be used as a baseline.
 - Blood cultures: cultures of two recent (different site) blood microbiology samples collected prior to the time of first administration of study drug will be selected. Isolates from the cultures of both of these 2 blood microbiology samples will be used as a baseline. Culture results from blood microbiology samples collected from two different sites within 48h prior to randomization are acceptable. Isolates from blood microbiology samples assessed as contaminated will not be used as baseline.
- For post-baseline values:
 - Lower respiratory sample cultures: the results of all sample cultures collected within the nominal visit will be used.
 - Blood cultures: the results of all cultures of samples collected within the nominal visit will be used.

